1. ALICE PDX

2. WP200

Shown above are pictures of the two validated and non-invasive portable monitors that will be used during this study. They will yield equivalent results that are comparable PSG. Two monitors are chosen for efficiency of screening as 1 of each is available to the PI. The PSG has to follow the PM test as it will serve as the confirmatory gold standard diagnostic test and will allow for titration of AUTOPAP treatment.

[figure not shown]
URINE SAMPLE

Urine Samples for Sympathetic Nervous System Activity: Patients will provide urine samples collected over 24 hours as two samples (after first void in the morning to 10 PM and from 10 PM to first void the morning). The overnight samples will be collected on ice 24-hour urinary excretion of catecholamines (SNA) will be measured from the pooled sample

The samples will be homogenized into aliquots of 50 ml. The catecholamine assay will be performed per the UIC Clinical Science Building.

The assay analysis of the urine will be done at the UIC Clinical Science Building because the turnaround time is quicker at the same cost. Samples will be analyzed for norepinephrine and 3-methylnorepinephrine (normetanephrine) using high performance liquid chromatography (HPLC) with electrochemical detection and expressed in $\mu\text{mol}\cdot\text{mol}^{-1}$ of creatinine⁸³. HPLC offers the advantage that commonly used anti-hypertensive drugs do not interfere with the results.

Urine Samples for 8-isoprostane: (oxidative stress related to OSA) from the overnight samples.

Total (free + esterified) isoPs will be analyzed. Esterified isoP-containing lipids in urine (0.5 mL) will be hydrolyzed with β -glucuronidase from *Helix pomatia* (10 μL , 100 units/ μL) at 37 $^{\circ}\text{C}$ under argon for 20 h. Lipid hydrolysis will be conducted in the presence of [2H11]-iso-PF2 α -VI, [2H11]-8,12-iso-PF2 α -VI, [2H4]-8-iso-PGF2 α , [2H9]-PGF2 α , and [2H4]-11 β -PGF2 as stable isotopically-labeled internal standards (10 ng of each), butylated hydroxytoluene (to prevent autoxidation) and deferoxamine (to prevent Fenton chemistry). The free isoprostanes that are released together with free isoPs that were present original in the urine (total isoPs) will be analyzed by negative ion LC-SRM/MS (Figure x). The assay will simultaneously analyze the four major isoprostanes found in serum lipids (iso-PF2 α -VI, 8,12-iso-PF2 α -VI, 8-iso-15(R)-

PGF_{2a}, and 8-iso-PGF_{2a}), as well as PGF_{2a}, and 11 β -PGF₂. After hydrolysis, the urine will be diluted with 1 M phosphate buffer pH 6.8 (1 mL) and acidified to pH 5.5 with 1 M formic acid. Lipids will be extracted with methyl tertiary-butyl ether/hexane, the organic layer evaporated to dryness, the residue re-constituted in 30 % aqueous acetonitrile (50 μ L). An aliquot (10 μ L) will be analyzed by LC-SRM/MS under negative electrospray ionization conditions using the transitions shown in Figure above. Chromatography will be conducted on a Phenomenex KinetexXB C18 (2) column (150 x 2.1 mm internal diameter, 2.6 μ m, 100 \AA). A linear gradient will be used with a mobile phase of water with 2 mM ammonium hydroxide and acetonitrile and a flow of 0.2 mL/min.

**APPENDIX III: BLOOD SAMPLING WITH DNA, RNA, SERUM, and PLASMA
PROCESSING AND STORAGE**

A single venous blood sample of approximately 35 ml or two tablespoons will be collected during visit 1 and visit 5. Samples will be transported with labels that state study ID together with a sample requisition form (with title of study, name of PI and coordinator, date of collection, and number and types of test tubes delivered; see below). These samples will be processed as specified below and stored indefinitely at UI Biorepository. These samples will remain linked to clinical information gathered for research by study ID, which will be maintained indefinitely at the UI Biorepository.

REQUISITION FOR LABORATORY SERVICES		
STUDY TITLE : Targeted Treatment of Obstructive Sleep Apnea to Reduce Cardiovascular Disparity		
IRB Protocol # _____		
Patient Study ID: _____		
Performance Site (circle one): Jesse Brown VA Medical Center		
Contact: [name] [contact], [contact]		
Collection Date: _____ Collection Time: _____		
Approved Test: mark all appropriate		
     	Test Name Serum DNA PBMC Plasma	Tube ↑ 1 Red Top, 5ml 3 Purple Top, 6ml 1 Pax Gene ↓
*Top 4 boxes should always be marked		
**RRC Contact Info: [contact] / [contact]		
Delivered to RRC (CSBN W-17)? Yes _____ Time of delivery _____ No _____ If no, why? _____		

24-hour urine REQUISITION FOR LABORATORY SERVICES		
STUDY TITLE: Targeted Treatment of Obstructive Sleep Apnea to Reduce Cardiovascular Disparity		
IRB Protocol # _____		
Patient Study ID: _____		
Performance Site (circle one): Jesse Brown VA Medical Center		
Contact: [name] [contact], [contact]		
Collection Date: _____ Collection Time: _____		
Approved Test: mark all appropriate		
	Test Name	Tube
	Dopamine	↑
	Norepinephrine	2 6ml tubes on dried ice
	epinephrine,	↓
		
		
*Top 3 boxes should always be marked		
[name] contact info: [contact]		
Deliver to CSB (room 215)  Yes  No  Time of delivery _____ If no, why? _____		
CSB Staff Initials _____		

The processing and storage will be performed at UI biorepository per protocol specified below.

Five tubes of blood will be collected; these include two 8-ml BD Vacutainer® CPT Mononuclear Cell Preparation Tube for the isolation of lymphocytes and monocytes, two 6-ml purple top vacutainers (K₂EDTA additive) for plasma and DNA recovery, and one 6-ml red top vacutainer (no additives) for serum recovery. These samples will be collected and stored at room temperature until processing. Processing for all derivatives will be performed within four hours of the initial blood draw.

Whole blood collected in the CPT vacutainers will be centrifuged according to the manufacturer's instructions, and after the centrifugation, the overlying plasma will be decanted. The buffy coat remaining above the gel barrier will be removed from the two CPT vacutainers and transferred to a sterile 50-ml tube and washed with Hank's Buffered Salt Solution (HBSS). At this point, Peripheral blood mononuclear cell (PBMC) number will be measured using a Millipore Scepter Handheld Automated Cell Counter. The PBMCs will then be pelleted by centrifugation, and the HBSS removed. The PBMCs will then be lysed in 2 ml of TRIzol solution and stored at -80C in a sterile 2-ml 2D barcoded tube.

Blood from the two purple top vacutainers will be fractionated as following: Duplicate DNA extractions will be performed on 350 microliters of whole blood using the iPrep Purification Instrument with the iPrep™ PureLink™ genomic DNA (gDNA) Blood kit (Invitrogen). The gDNA will be eluted in 200 microliters of buffer, analyzed using a NanoDrop 1000 spectrophotometer and aliquoted. Six aliquots of 30 microliters will be produced for future distribution, and one aliquot of 200 microliters (likely 10-20 micrograms of DNA) will be retained for future whole genome sequencing, if requested. These will be stored in sterile, barcoded tubes of 0.5-ml volume. In addition, 750 microliter aliquots of whole blood will be stored in sterile, barcoded tubes of 1-ml volume. The remaining whole blood will be centrifuged at 4°C for 10 minutes at 1,500 RPM, and the overlying plasma will be recovered and aliquoted into six 1-ml barcoded tubes.

Blood from the single red top vacutainer will be stored at room temperature for 15 minutes before centrifugation at 4°C for 10 minutes at 1,500 RPM. Subsequently, the overlying serum will be recovered and aliquoted into four 1-ml barcoded tubes.

In total, 20 tubes of derivatives of whole blood will be generated: (1) 2-ml tube with PBMCs in TRIzol, (2) 0.75-ml whole blood in 1-ml tubes, (6) 0.03-ml gDNA in buffer in 0.5-ml tubes, (1) 0.2-ml gDNA in buffer in a 0.5-ml tube, (6) 0.50-ml plasma in 1.0-ml tubes and (4) 0.50-ml serum in 1.0-ml tubes.

Gene and microRNA Expression Profiling- This proposal will utilize the GeneChip® Human Gene 1.0 ST Array by Affymetrix (details at the website) for gene expression profiling, covering > 28,869 genes represented on the array by approximately 26 probes spread across the full length of an individual gene. The Human Gene 1.0 ST Array has greater than 99 percent coverage of

sequences present in the RefSeq database. To determine microRNA differences, this proposal plans to use the mercury LNA microRNA array offered by Exiqon. The array provides access for examination of over 1300 human microRNAs with as little as 30ng total RNA. RNA for both of these arrays will be isolated from the blood collected from these patients in this study as described earlier. Details of this technology are also provided at <http://www.exiqon.com>.

3) Serum specimens

Serum specimens are primarily collected for future proteomics analysis. At this stage of planning, specimens are prepared anticipating subsequent analysis by a modified form of Isotope Coded Affinity Tagging. As new techniques become available or new biomarkers are identified, these specimens may be analyzed by alternative methods.

One 8 ml red-top tube specimen will be centrifuged at room temperature at approximately 1000 x g for 5 minutes. The serum supernatant will be removed and stored at -80°C in 125 μl aliquots.

4) Plasma specimens

Plasma specimens are primarily collected for conventional analysis by immunosorbent or biochemical assay. As platelet contamination, proteolysis and other aspects of handling can contribute to variable assay results, specimens will be handled according to the following protocol. The technician will retrieve one 4 ml lavender-top tube and centrifuge for 15 minutes at 4°C at 1000 x g within 30 minutes of collection. The plasma supernatant will be removed to a fresh tube and centrifuged an additional 10 minutes at 1000 x g before removal and storage by the same method for the serum above.

5) AIMs analysis in isolated DNA at [name] laboratory

Autosomal SNP AIMs will be genotyped using the Sequenom MassARRAY™ platform and iPLEX™ chemistry. Individual Ancestry will be estimated from the genotype data using the Bayesian Markov Chain-Monte Carlo (MCMC) method implemented in STRUCTURE version 2.1. STRUCTURE will be run under the admixture model using prior population information and independent allele frequencies. The MCMC method will be run using K=2 and K=3 parental populations and a burn-in length of 30,000 for 70,000 repetitions. The best model of K to use will be determined and principal components based on the total AIMs using EIGENSTRAT will be computed.

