Sleepiness Score (ESS) questionnaire, Functional Outcomes of Sleep Questionnaire (FOSQ), complete medical history and physical examination, and CABP measurements. Enrollment of patients who have severely elevated blood pressure (>200/120 mm Hg) will be deferred and they will be referred to their primary care provider/urgent care as clinically appropriate.

All antihypertensive medications will be recorded (number, dose, and refill information) for each patient at baseline and at the end of the study (final visit). This information will be confirmed with the JBVAMC/or outside pharmacy for accuracy. Patients will be encouraged to follow up with primary physician per usual schedule and to avoid taking over-the-counter medications that may affect blood pressure (e.g., some cold medications) for 24 hours before and during the ABP monitoring.

All eligible patients will perform a 10-minute psychomotor vigilance task (PVT). Specifically, consenting patients will have venous blood sampling (35 mL) for processing (DNA, RNA, serum, and plasma) and storage at UI Biorepository as well as an echocardiography scheduled at JBVAMC. A urine pregnancy test will be done for women of childbearing potential. All enrolled patients will initiate 7-day actigraphy with concurrent sleep logs (to estimate average nightly sleep duration), 24-hour urine collection, and 24-hour ABP recordings at completion of visit 1 and will be scheduled for an overnight portable monitoring (PM) test at Jesse Brown VAMC (Visit 2) or at home. If the PM test fails to record data due to technical or application errors, the patients may be asked to repeat this test once. We will schedule an echocardiography test at JBVAMC for consenting patients (to be completed before visit 4).

Each measure to be performed is briefly described below. All are validated and commonly used in clinical practice and research:

- i. **PVT:** A 10-minute PVT192 test with a hand-held device for sustained attention will be conducted (Ambulatory Monitoring, Inc., Ardsley, NY), with a preceding 1-minute practice exercise. Participants will be using the hand held device and respond to the stimuli presented on the screen at random intervals by pressing a button. The PVT indicator of EDS will be frequency of lapses (instances where the patient fails to respond to the stimulus in a timely manner; Reaction Time, RT > 500 milliseconds).

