Tissue banking: blood processing for DNA, RNA, serum and plasma isolation and storage will be performed at UI Biorepository, under the supervision of [name], [name] and [name] (Clinical Science Building North, [name]). The blood samples to be carried outside JBVAMC will be labeled with unique study ID number only. Only the processing of blood will be done outside JBVAMC and the blood draw procedure will only be done at JBVAMC. The processing for JBVAMC is done at the Madison/Milwaukee VA lab. To avoid delays loss of sample or sample integrity, we want to hand-deliver the samples without individual identifiers to UIC for prompt processing.

- viii. **Echocardiogram** data will include myocardial mechanical data obtained by clinical software that is used in the clinical workstation in the JBVAMC echocardiography laboratory. This software is called Velocity Vector Imaging (VVI; Siemens Medical Solutions USA, Inc., Mountain View, CA). [name], JBVAMC cardiologist and collaborator will provide interpretation of these data.

Visit #2: Patients performing home PM will be instructed to begin ABP monitoring and urine sample collection the morning prior to the scheduled visit 2. Visit 2 will be in the morning and PM device, actigraphy, sleep log, urine sample, and ABP monitor will be collected and processed/downloaded. Patients performing PM test at JBVA will be instructed to begin ABP monitoring and urine collection the morning of scheduled visit 2. Patients will arrive for the overnight PM at JBVAMC. Actigraphy, sleep log, urine sample, and ABP monitor will be collected and processed/downloaded in the morning after completion of the PM test. PM tests will be performed using ALICE PDX (Phillips Respironics) or WatchPAT200 (Itamar Medical). PI has experience with both these devices that are available to us, are validated, used routinely in

clinical practice, and provide similar information with respect to screening for OSA. All patients with apnea hypopnea index (AHI) ≥ 15 /hour on the PM test will be invited to continue. This additional screening step with PM testing will reduce screen failure rates with PSG, which is more costly. We propose to allow both home PM and PM at JBVAMC in order to minimize scheduling conflicts between clinical and research tests scheduled.

Previously scheduled Visit 3 will be eliminated to reduce participant burden and improve recruitment to meet target sample of 220 over the next two years.

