9.4 Statistical Analyses

9.4.1 Power and Sample Size Estimation: The primary goal of this initial study is to estimate differences in the effect size of AUTOPAP treatment on ABP and CABP in AA and EA's with moderate to severe OSA. Our preliminary data shows a reduction in office BP 3 months after AUTOPAP treatment and the effect size difference between-groups (by ethnicity; using differences in mean \pm SD change of BP and t-tests in PASS program, <http://www.ncss.com/pass.html>) was 0.42 for systolic and 0.53 for diastolic blood pressure. We determined that 99 patients in each group (total n = 198) will provide power of 0.8 in two-tailed tests with an alpha of 0.05 to observe a difference in effect size between groups of 0.4. Based on our prior experience we anticipate an attrition rate of 10-20%. Therefore, a total of 220 (198/0.90) patients enrolled will achieve the target of 198 patients completing the study. Our preliminary study of PM in our clinical population (selected with a positive BSQ) shows approximately 95% sensitivity and specificity of PM determined AHI of ≥ 15 /hour in terms of predicting PSG-determined AHI of ≥ 15 /hour (inclusion criteria). Therefore, we expect to screen approximately 260 patients (220/0.95).

9.4.2 Data analysis: A p-value < 0.05 will be considered significant. All variables and analysis goals are listed in table above. **Specific Aim 1.** Within group changes in primary and secondary outcomes will be assessed with repeated measures ANOVA implemented with PROC MIXED in SAS. A two-sample t-test (PROC TTEST in SAS) will be used to examine between-group differences in the treatment-related changes in primary and secondary outcomes. **Specific Aim 2.** Primary outcome will be assessed with a two-sample t-test (PROC TTEST in SAS). Secondary outcomes will be assessed with partial correlations implemented with PROC CORR in SAS.

Exploratory Aims 3. Effect of Individual Ancestry on changes in primary and secondary outcomes of specific aim 1 within group will be assessed with ANCOVA implemented with PROC GLM in SAS. Correlations (of VVI with AHI and change in VVI with change in AHI) will be assessed within groups.

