APPENDIX I: SCHEDULE OF EVENTS

Table. Patient Schedule						
Procedures	Visits					
	1	2	3	4	5	6
Week	0-2			3-16		
Informed consent	x					
History and physical, anthropometrics	x					
Home portable monitoring (PM) test	x					
Determine AHI at termination of PM (≥ 15 /hour; enrolled)		x				
Central aortic blood pressure measurement (with brachial cuff), PVT x 2	x	x			x	
Venipuncture for blood sample (genotyping for AImS)		x			x	
Start 7-day actigraphy recording with sleep log		x			x	
Initiate 24-hour urine collection		x			x	
Initiate 24-hour ABP		x			x	
Collect and process: 24-hour urine, 24-hour ABP			x			x
Download 7-day actigraphy recording			x			x
Initiation of AUTOPAP with subject education				x		
Telephone contacts for AUTOPAP adherence optimization	Twice weekly x 4, then once/week					
Schedule Echocardiography		x			x	
Final visit and AUTOPAP adherence data download						x

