APPENDIX IV: HUMAN SUBJECTS

A. Risks to Subjects

A.1 Human Subjects Involvement and Characteristics

After completing the informed consent process, the proposed study will enroll a total of 220 self-identified African American and Other(race), Veterans with pre-existing hypertension and newly diagnosed (and treatment-naïve) moderate to severe obstructive sleep apnea. These adult Veterans will not have debilitating physical or mental health problems. We will not recruit pregnant women, children, prisoners, institutionalized individuals, or other vulnerable populations. During preliminary screening, subjects will be informed of the study purpose, the risks and benefits pertaining to their participation, the enrollment process, the proposed testing, and the necessary time commitment.

Inclusion criteria briefly noted above are summarized in section C.4 (Table 7) of the research plan for this proposal. *Exclusion criteria* include: 1. Past/current treatment of OSA or other primary sleep disorders; 2. Active uncontrolled medical conditions; 3. Shift work in past 6 months; 4. Current drug use, and pregnancy. At screening visit blood sample (15 ml, for genetic ancestry testing), urine pregnancy test (if applicable), and disease specific screening questionnaires, and a brief vigilance test with a hand-held device will be obtained. In addition, information regarding personal and family medical history, medication use, sleep-wake schedule and work schedule will be collected, and a physical examination will be performed. The physical examination will include central aortic blood pressure measurement (performed with a cuff on the upper arm) similar to the process utilized routinely in clinical practice. All subjects with baseline peripheral blood pressure values of > 180 mm Hg systolic or > 110 mm Hg diastolic will be referred for urgent medical care and their enrollment will be deferred until medically cleared by their primary care provider.

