All eligible subjects will undergo standard clinical care and research related procedures: (1) polysomnography for diagnosis of obstructive sleep apnea and confirmation of disease severity, (2) 7-day actigraphy, 24-hour ambulatory blood pressure monitoring, and 24-hour urine sample collection, Epworth sleepiness questionnaire, and a psychomotor vigilance test will be performed at baseline (pre-treatment) and three months after institution of treatment for obstructive sleep apnea, (3) standard treatment of obstructive sleep apnea i.e., polysomnography guided continuous positive airway pressure device treatment will be provided to all subjects. All research related subject visits will take place at the Jesse Brown VAMC.

A.2 Potential Risks

General: We see no psychological, social or legal risk associated with this research, beyond those of participation in health-related research in general.

Blood sampling: There is a small risk of local hematoma (1 in 10 cases), and an extremely small risk (1 in 1000 cases) of infection associated with insertion of needles for blood withdrawal. An experienced technician, using aseptic techniques, will minimize these risks.

Urine collection: No risks are identified except loss of confidentiality (addressed below).

Polysomnography: Is a routine laboratory-based procedure attended by a trained technologist. Minor skin irritation may occur from the electrode's application, in addition to fragmentation of sleep. These complications are rarely observed, and every effort will be made to minimize the associated discomfort.

Actigraphy: Is a wrist-watch and maybe associated with minor skin irritation and wrist discomfort.

24-ambulatory blood pressure monitoring with an inflatable cuff on the non-dominant upper extremity: The monitor itself is light and fits inside a shirt pocket. The cuff inflations can cause local discomfort. Therefore, we will limit our sampling rate to every 20 minutes during the day and every half-hour at night.

Central aortic blood pressure measurement will be performed non-invasively with a cuff on the subject's upper arm that is inflated briefly. This cuff is attached to a special monitor (Sphygomocor). The procedure in terms of subject risk is the same as a regular blood pressure check in their doctor's office.

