Continuous Positive Airway Pressure (AUTOPAP) device treatment: Is the first-line treatment for obstructive sleep apnea and its safety and efficacy are well established. Complications skin irritation of the face at the site of mask application, nasal congestion/oral dryness, and claustrophobia. We will use standard measures used to address these issues promptly, such as individualized education, mask-fitting, and use of heated humidity.

Confidentiality: It is possible that subject confidentiality could be breached. However, all data will be coded and direct linkages between the subject and the data from that subject will be broken once the necessary clinical information has been obtained. No publications lists or stored data will directly link a study subject with his or her data.

A.3 Sources of Material

The research data for Aim 1, 2, and 3 include questionnaire data, medical histories, physical examination and measurements, blood and urine tests, polysomnography, actigraphy, and 24-hour ambulatory blood pressure monitoring. A portion of the urine sample will be collected on ice and carried by study coordinator to JBVAMC room 7200, Taylor Pavillion to be stored in -80 degrees Celsius freezer for later systemic oxidative stress biomarker measurement. The single blood draw of 35 ml will be carried by study coordinator to UI Biorepository, Clinical Science Building North [name] for DNA, RNA, serum, and plasma processing and storage. The DNA data generated will be hand carried by PI/study coordinator to UIC Institute of Human Genetics at 3302 MBRB, MC 767, [name] for genetic ancestry analysis. All data collected will be securely stored, de-identified, and used for research purposes only.

A.4 Therapeutic Risk

The treatment intervention (AUTOPAP) is the standard treatment for sleep apnea of all severity. Therefore, the risks incurred are no more than in routine clinical care and include complications skin irritation of the face at the site of mask application, nasal congestion/oral dryness, and claustrophobia.

Polysomnography will be performed once (for diagnosis confirmation and AUTOPAP titration) as is done in routine clinical practice. Minor skin irritation may occur from the electrode's application, in addition to fragmentation of sleep.

A.5 Research Risk

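### The optional research blood draw is taken at Visit 1, before AHI eligibility is known; Appendix I places it at visit 2, and the risk section (Appendix IV) gives too little blood and omits the repeat draw

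*Combined protocol and SAP*

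**What the plan says.** **Baseline draw.** Under Visit 1, Section 3 says that "consenting patients will have venous blood sampling (35 mL) for processing (DNA, RNA, serum, and plasma) and storage at UI Biorepository", and the synopsis says the same. Appendix III gives the volume and both visits: "A single venous blood sample of approximately 35 ml or two tablespoons will be collected during visit 1 and visit 5".

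**Eligibility.** Portable monitoring is arranged at Visit 1 and read at Visit 2, where Section 3 says: "All patients with apnea hypopnea index (AHI) ≥ 15 /hour on the PM test will be invited to continue".

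**Schedule table.** In Appendix I the row "Venipuncture for blood sample (genotyping for AImS)" is marked at visits 2 and 5. Visit 2 is also the column in which AHI is determined and the patient counts as enrolled. Consent is at visit 1.

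**Risk section.** Appendix IV A.1 reads "At screening visit blood sample (15 ml, for genetic ancestry testing)". A.3 reads "The single blood draw of 35 ml will be carried by study coordinator to UI Biorepository".

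**Repeat draw.** Section 2.3 and Appendix III put it at visit 5. The synopsis and Section 3 put it under Visit 4.

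**Consent and storage.** The draw has its own consent and can be declined without leaving the primary study (synopsis, Section 3). Samples are kept indefinitely (Section 11.3) and stay linked to clinical data by study ID (Appendix III).

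**The concern.** There are two separate problems.

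The first is timing. A Veteran who consents to banking and then records an AHI below 15 has already been bled. Appendix IV A.2 describes the procedure thus: "There is a small risk of local hematoma (1 in 10 cases)". That person is never treated and has no 3-month outcome, so the sample serves neither use the plan describes for it, yet it is stored without limit. No section says what happens to such samples. Nor can staff follow both Section 3 and Appendix I on when to draw.

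The second is disclosure of volume. Appendix IV is where burden and risk are set out for review. It gives two different figures, and neither describes the two-draw plan found elsewhere.

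What is at stake is participant burden, the accuracy of the risk section and consistent conduct. The comparison of blood pressure change between groups is not touched.

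**Working it through.** **1. Volume per draw.** The tube list in the processing text of Appendix III has two 8-ml CPT tubes, two 6-ml purple-top tubes and one 6-ml red-top tube:

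2 × 8 + 2 × 6 + 1 × 6 = 34 ml.

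This reproduces the stated 35 ml to within 1 ml (1/35 = 2.9%). Appendix III's per-draw volume is therefore sound.

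**2. Total planned.** Two draws: 2 × 35 = 70 ml (2 × 34 = 68 ml by the tube list).

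**3. Appendix IV against that.**
- A.1 refers to the screening visit only, so the fair comparison is one draw: 35 − 15 = 20 ml short. The 15 ml is labelled for ancestry testing, but A.3 takes the ancestry DNA from the 35 ml draw, so 15 ml matches no other section.
- A.3 has the right volume for one draw. Appendix IV never mentions a second. A.1 lists the measurements made at baseline and again at three months (actigraphy, ambulatory pressure, urine, Epworth, PVT) and leaves blood out. A.5 says ambulatory monitoring is done twice. The appendix thus counts repeats for other procedures but not for venipuncture.

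**4. Timing, side by side.**

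| Source | Baseline draw | AHI known | Repeat draw |
|---|---|---|---|
| Synopsis | Visit 1 | Visit 2 | Visit 4 |
| Section 2.3 | not stated | not stated | visit 5 |
| Section 3 | Visit 1 | Visit 2 | Visit 4 |
| Appendix I | visit 2 | visit 2 | visit 5 |
| Appendix III | visit 1 | not stated | visit 5 |
| Appendix IV A.1 | screening visit | not stated | none mentioned |

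**5. Does renumbering explain it?** Section 3 says a former Visit 3 was dropped. Appendix I still has six visits and starts AUTOPAP at visit 4; Section 3 starts it at Visit 3. That shift could explain a repeat draw labelled visit 5 in one place and Visit 4 in another: Appendix I starts the follow-up ambulatory recording at visit 5, and Section 3 does so at Visit 4. It cannot explain the baseline conflict, because dropping Visit 3 leaves Visits 1 and 2 as they were. Appendix I puts consent and the draw at different visits, while Section 3 puts them at the same one.

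**6. Can the plan use blood from Veterans with AHI below 15?** The ancestry aim relates ancestry to change in blood pressure after treatment (synopsis objective 5; Section 9.4.2). Section 2.3 justifies banking by treatment-related genomics with a repeat sample at the end of treatment. Both need a treated patient with follow-up.

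**The case against.** **The draw is optional, and early grouping is a legitimate choice.** It is separately consented, and the synopsis objective for banking speaks of future genomic studies without an AHI limit. PVT, ambulatory pressure, urine and actigraphy also begin at Visit 1, before AHI is known, and the plan is openly concerned with participant burden. This stands in part. A reader might infer that ineligible Veterans are bled needlessly; the documents show only that no use is stated for their samples, not that none is possible.

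**The schedule conflict is not specific to blood.** Appendix I shows the same visit 1 to visit 2 shift for ambulatory pressure, urine and actigraphy. True, but it does not remove the conflict for the draw.

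**The number affected is not known.** Section 9.4.1 says "we expect to screen approximately 260 patients", so it is tempting to count 260 − 220 = 40 ineligible Veterans, or 220/0.95 = 232 and 232 − 220 = 12, and to turn these into about 1 to 4 hematomas at the 1-in-10 rate. The documents do not support this. The 0.95 is the sensitivity and specificity of portable monitoring against polysomnography, not the share of those screened who reach AHI 15, and the polysomnography step has been dropped. The 260 also does not follow from the division printed beside it. The counts would further require every ineligible Veteran to accept an optional draw.

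**The volume gap can be exaggerated.** Setting 15 ml against 70 ml gives a 55 ml shortfall, but compares one visit with the whole study. In A.3 the word single can mean one per visit, as it does in Appendix III. That reading is fair, yet Appendix IV still never discloses a second draw.

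**Consent.** The consent form was not in the text reviewed, so nothing can be said about what participants were told.

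**Conclusion.** The point holds as a minor one. The documents disagree on when the baseline research draw is made, and three of the four sections that name a numbered visit for it (synopsis, Section 3 and Appendix III) place it before eligibility is known. The result is a venipuncture and indefinite storage, with no stated use, for consenting Veterans who then fail the AHI criterion. The number of such Veterans cannot be derived from the plan.

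Appendix IV is 20 ml too low for the screening draw and silent on the repeat draw; the planned total is about 70 ml. That total assumes the patient consents to banking and completes both draws.

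A reader might also infer that the before-and-after samples are in danger because A.3 speaks of a single draw. They are not: the synopsis, Sections 2.3 and 3, and Appendices I and III all plan the repeat. Primary analysis, alpha, power and sample size are unaffected.

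**What to change.** 1. Take the baseline research draw once AHI of at least 15 is confirmed and before AUTOPAP starts, for example at the existing set-up visit. By the synopsis, Visits 1 to 3 span 7 to 10 days, so the sample stays a true pre-treatment one. Use this timing in the synopsis, Section 3, Appendix I and Appendix III, and align the screening-visit wording in Appendix IV A.1.
2. Correct Appendix IV A.1 and A.3 to two draws of about 35 ml, about 70 ml in total.
3. In the same edit, give the repeat draw one visit label throughout (Visit 4 in the synopsis and Section 3; visit 5 in Section 2.3, Appendix I and Appendix III).
4. Align the requisition form in Appendix III with the tube list. It shows 1 × 5 + 3 × 6 = 23 ml plus one Pax Gene tube of unstated volume, and no CPT tubes.

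The cost is amendment wording. No visit or procedure is added, and fewer samples are processed. The small loss is banked blood from screen failures. If the sponsor wants those samples, it should state the purpose and a rule for keeping or destroying them.
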